#### 7.2.2.2. Summaries of Laboratory Abnormalities

Laboratory data that are categorical will be summarized using the number and percentage of subjects in the study with the given response at predose and each scheduled postdose visit.

The following summaries (number and percentage of subjects) for treatment-emergent laboratory abnormalities will be provided by lab test and hepatic function group; subjects will be categorized according to the most severe postdose abnormality grade for a given lab test:

- Graded laboratory abnormalities
- Grade 3 or 4 laboratory abnormalities

For all summaries of laboratory abnormalities, the denominator is the number of subjects with nonmissing postdose values up to 30 days after last dosing date.

A by-subject listing of treatment-emergent laboratory abnormalities will be provided by subject ID number and visit in chronological order. This listing will include all test results that were collected throughout the study for the lab test of interest, with all applicable severity grades displayed.

#### 7.3. Vital Signs

Descriptive statistics will be provided by hepatic function group for vital signs as follows:

- Predose value
- Values at each postdose visit
- Change from predose at each postdose visit

Predose and postdose values will be defined as described in Section 3.7.1. Change from predose to a postdose visit will be defined as the postdose value minus the predose value.

In the case of multiple values in an analysis window, data will be selected for analysis as described in Section 3.7.3. No formal statistical testing is planned.

A by-subject listing of vital signs will be provided by subject ID number and visit in chronological order.

#### **7.4. Prior and Concomitant Medications**

Medications collected at screening and during the study will be coded using the current version of the World Health Organization (WHO) Drug dictionary.

A summary of prior and concomitant medications will not be provided.

All prior and concomitant medications (other than per-protocol study drugs) will be provided in a by-subject listing sorted by subject ID number and administration date in chronological order.

#### **7.5. Investigator Electrocardiogram Assessment**

A shift table of the investigators' assessment of ECG results at each visit compared with predose values will be presented by hepatic function group using the following categories: normal; abnormal, not clinically significant; abnormal, clinically significant; or missing. The number and percentage of subjects in each cross-classification group of the shift table will be presented. Subjects with a missing value at predose or postdose will not be included in the denominator for percentage calculation. No formal statistical testing is planned.

A by-subject listing for ECG assessment results will be provided by subject ID number and visit in chronological order.

#### **7.6. Other Safety Measures**

A by-subject listing of subject pregnancies during the study will be provided by subject ID number. No additional safety measures are specified in the protocol.

Although not necessarily related to safety, a by-subject listing of all comments received during the study on the comments form will be provided by subject ID number, and form for which the comment applies.

#### **7.7. Changes From Protocol-Specified Safety Analyses**

There are no changes from the protocol-specified safety analyses.

## 8. PHARMACOKINETIC EVALUATION/ANALYSIS

### 8.1. Estimation of Pharmacokinetic Parameters

PK parameters will be estimated using Phoenix WinNonlin® software using standard noncompartmental methods. The linear up/log down rule will be used in conjunction with the appropriate noncompartmental model, with input values for dose level, dosing time, plasma concentration, and corresponding real-time values, based on drug dosing times whenever possible.

All predose sample times before time-zero will be converted to zero.

For area under the curve (AUC), samples below the limit of quantitation (BLQ) of the bioanalytical assays occurring prior to the achievement of the first quantifiable concentration will be assigned a concentration value of zero to prevent overestimation of the initial AUC. Samples that are BLQ at all other time points will be treated as missing data in WinNonlin. The nominal time point for a key event or dosing interval ( $\tau$ ) may be used to permit direct calculation of AUC over specific time intervals. The appropriateness of this approach will be assessed by the PK scientist on a profile-by-profile basis.

Pharmacokinetic parameters such as  $AUC_{inf}$ ,  $\lambda_z$  and  $t_{1/2}$  are dependent on an accurate estimation of the terminal elimination phase of drug. The appropriateness of calculating these parameters will be evaluated upon inspection of PK data on a profile-by-profile basis by the PK scientist.

### 8.2. Pharmacokinetic Parameters

Pharmacokinetic parameters will be generated for all subjects for whom parameters can be derived. The analytes presented in [Table 8-1](#) will be evaluated if data are available.

**Table 8-1. Study Treatments and Associated Analytes**

Cohort	Treatment	Analytes
1 and 2	A single oral dose of GS-9674 30 mg (3 × 10 mg tablet) administered on Day 1	GS-9674 and its metabolite GS-716070, GS-1056756 and GS-1056757, as applicable
3	A single oral dose of GS-9674 10 mg (1 × 10 mg tablet) administered on Day 1	GS-9674 and its metabolite GS-716070, GS-1056756 and GS-1056757, as applicable

The analytes and parameters presented in [Table 8-2](#) will be used to evaluate the PK objectives of the study. The primary PK parameters are  $AUC_{last}$ ,  $AUC_{inf}$ , and  $C_{max}$  of GS-9674. The PK parameters to be estimated in this study are listed and defined in the Pharmacokinetics Abbreviations section.

**Table 8-2. Pharmacokinetic Parameters for Each Analyte**

Analyte	Parameters
GS-9674, and its metabolite GS-716070, GS-1056756 and GS-1056757, as applicable	%AUC exp , AUC last *† , AUC inf *† , C max *† , C last , T max , T last , λ Z , CL/F † , V Z /F, and t 1/2 , as appropriate

\* Parameter used in sample size and power calculations.

† May be calculated as both total and unbound.

### 8.3. Statistical Analysis Methods

#### 8.3.1. General Considerations

Individual subject concentration data and individual subject PK parameters (including percentage of protein binding) for GS-9674, GS-716070, GS-1056756 and GS-1056757 will be listed and summarized using descriptive statistics by hepatic function group within cohort. Summary statistics (numbers of subjects, mean, SD, coefficient of variation [%CV], median, minimum, maximum, Q1, and Q3) will be presented for both individual subject concentration data by time point and individual subject PK parameters by hepatic function group within cohort. Moreover, the geometric mean, 95% CI, and the mean and SD of the natural log-transformed values will be presented for individual subject PK parameter data.

The percentage unbound fraction ( $f_u$ ) for each analyte (where applicable) will be estimated by averaging the percentage unbound in plasma from 3 hour postdose, 5 hour postdose, and spike-in samples. Individual subject unbound PK parameter estimates for AUCinf, AUClast, Cmax may be calculated using PK parameter estimates multiplied by  $f_u$ . The unbound CL/F may also be calculated by using the estimated CL/F divided by  $f_u$ .

Individual concentration data listings and summaries will include all subjects with concentration data. The sample size for each time point will be based on the number of subjects with nonmissing concentration data at that time point. The number of subjects with concentration BLQ will be presented for each time point. For summary statistics, BLQ values will be treated as zero at predose and one-half of the lower limit of quantitation (LLOQ) for postdose time points.

Individual PK parameter data listings and summaries will include all subjects for whom PK parameters can be derived. The sample size for each PK parameter will be based on the number of subjects with nonmissing data for that PK parameter.

The following tables will be provided for each analyte by hepatic function group within each cohort:

- Individual subject concentration data and summary statistics
- Individual subject plasma PK parameters (total) and summary statistics

- Individual subject  $f_u$  and unbound PK parameters (as applicable) based on protein binding and summary statistics
- Percentage of unbound and bound GS-9674, GS-716070, and GS-1056756 at 3 hours postdose, 5 hours postdose, and spike-in samples
- Spearman's rank correlation coefficient between selected PK parameter estimates ( $AUC_{last}$ ,  $AUC_{inf}$ , and  $C_{max}$ ) and overall CPT Score, albumin, total bilirubin, prothrombin time, International Normalized Ratio, and serum creatinine

The following figures will be provided for each analyte by hepatic function group within each cohort:

- Individual subject concentration data versus time (on linear and semilogarithmic scales)
- Mean ( $\pm$  SD) concentration data versus time (on linear and semilogarithmic scales)
- Median (Q1, Q3) concentration data versus time (on linear and semilogarithmic scales)
- Scatter plots to show the relationship between dose-normalized PK parameter estimates ( $AUC_{inf}$ ,  $AUC_{last}$ , and  $C_{max}$ ) and overall CPT score, serum albumin, total bilirubin, prothrombin time, International Normalized Ratio, and serum creatinine. This set of plots may also be provided for overall enrolled subjects.

Individual, mean, and median postdose concentration values that are  $\leq$  LLOQ will not be displayed in the figures and remaining points connected. Dose normalization is calculated by dividing the PK parameter value by the ratio of the test dose/reference dose. The reference dose is 30 mg.

The following listings will be provided:

- PK sampling details by subject, including procedures, differences in scheduled and actual draw times, and sample age
- Individual data on determination of plasma half-life and corresponding regression correlation coefficient
- Individual data on protein binding

### **8.3.2. Statistical Methodology**

The statistical comparisons of the natural log-transformed PK parameters for each analyte and hepatic function group comparison of interest will be based on the PK analysis set for the analyte under evaluation. For each analyte, all subjects with available data for the PK parameter under evaluation will be included in the modeling.

Comparisons of interest are shown in [Table 8-3](#).

**Table 8-3. Statistical Comparisons for Pharmacokinetic Analyses of Normal and Impaired Hepatic Function**

Analyte	Parameter	Comparison	
		Test	Reference
GS-9674, GS-716070, GS-1056756 and GS-1056757	AUC last	Mild hepatic impairment	Matched normal hepatic function
	AUC inf		
	C max		
	AUC last	Moderate hepatic impairment	Matched normal hepatic function
	AUC inf		
	C max		
	AUC last	Severe hepatic impairment	Matched normal hepatic function
	AUC inf		
	C max		

For each analyte and each PK parameter within each cohort, a parametric (normal theory) ANOVA will be fitted to the natural log-transformed values of the single dose PK parameter under evaluation.

The statistical model will include hepatic function group as a fixed effect. The following SAS® PROC MIXED code will provide the comparison between the hepatic function groups and the 90% CI calculations for natural log-transformed PK parameters.

```
proc mixed;
  by cohort analyte paramcd;
  class hepaticgrp subjid;
  model lnest = hepaticgrp / ddfm=kr s;
  repeated / group=hepaticgrp;
  lsmeans hepaticgrp / e diff cl alpha = 0.1;
  estimate 'Mild impairment vs Normal' hepaticgrp 1 -1 / cl alpha = 0.1;
  (estimate 'Moderate impairment vs Normal' hepaticgrp 1 -1 / cl alpha = 0.1;)
  (estimate 'Severe impairment vs Normal' hepaticgrp -1 1 / cl alpha = 0.1;)
  ods output Estimates = LS_Diffs LSMeans = LS_Means CovParms = MSE;
run;
```

The ESTIMATE statement will be used to produce the point estimate and the corresponding 90% CI of the difference in PK parameters of interest on a logarithmic scale. The test-to-reference ratio and associated 90% CI will be calculated by exponentiation of the point estimate and the corresponding lower and upper limits, which is consistent with the two 1-sided tests approach {U.S. Department of Health and Human Services Food and Drug Administration Center for Drug Evaluation and Research (CDER) 2003}, {U.S. Department of Health and

Human Services Food and Drug Administration Center for Drug Evaluation and Research (CDER) 2001}.

If the upper bound of the 2-sided 90% CI of the GLSM ratio for  $AUC_{last}$ ,  $AUC_{inf}$ , and  $C_{max}$  is smaller than 2.0, we will reject the hypothesis that subjects with hepatic impairment exhibit average PK parameter (ie,  $AUC_{last}$ ,  $AUC_{inf}$ , and  $C_{max}$ ) increases of at least 100% for GS-9674 compared to subjects with normal hepatic function.

#### Nonparametric Analysis

Nonparametric analyses for the PK parameters (if calculated)  $CL/F$ ,  $V_z/F$ , and  $t_{1/2}$ , may be performed using the Wilcoxon rank sum test for parallel design between the test and reference groups for GS-9674, GS-716070, GS-1056756 and GS-1056757.

```
data param;  
  set adam.param;  
  where cohort=1 and analyte='GS-9674' and param='CL/F';  
run;
```

```
proc npar1way data=param wilcoxon;  
  class hepaticgrp;  
  var result;  
run;
```

#### 8.4. Sensitivity Analysis

Sensitivity analysis may be conducted for the key PK analyses if the PK scientist identifies PK data as questionable. The sensitivity analysis will exclude specific data from analyses, if appropriate. If a sensitivity analysis is deemed necessary, a listing of the PK parameter(s) data being excluded, with associated reason(s) provided by the PK scientist, will be generated.

## 9. PHARMACODYNAMIC EVALUATION/ANALYSIS

### 9.1. Estimation of Pharmacodynamic Parameters

PD parameters will be calculated for FGF19 and C4 on Days -1, and 1. In particular AUC calculations will be based on the linear trapezoidal rule, summing trapezoids over the particular time period (0 – 24 hours or x – y hours) on a particular day.  $C_{max}$ ,  $C_{min}$ ,  $T_{max}$ , and  $T_{min}$  will be determined empirically for the data.

### 9.2. Pharmacodynamic Parameters

PD parameters in

Table 9-1 will be generated for all subjects for whom parameters can be derived for biomarkers, FGF19 and C4, if data are available.

**Table 9-1. Pharmacodynamic Parameters for FGF19 and C4**

Day	Parameter
-1	$AUC_{0-24}$
1	$AUC_{0-24}$
1	$AUC_{0-24} \text{ ratio: } AUC_{0-24, (Day 1)} / AUC_{0-24, (Day-1)}$
-1	$AUC_{\text{Partial}}$
1	$AUC_{\text{Partial}}$
1	$AUC_{\text{Partial}} \text{ ratio: } AUC_{\text{Partial}, (Day 1)} / AUC_{\text{Partial}, (Day-1)}$
-1	$C_{\text{min}}$
1	$C_{\text{min}}$
1	$C_{\text{min}} \text{ ratio: } C_{\text{min}, (Day 1)} / C_{\text{min}, (Day -1)}$
-1	$C_{\text{max}}$
1	$C_{\text{max}}$
1	$C_{\text{max}} \text{ ratio: } C_{\text{max}, (Day 1)} / C_{\text{max}, (Day -1)}$
-1	$T_{\text{min}}$
1	$T_{\text{min}}$
1	$T_{\text{min}} \text{ ratio: } T_{\text{min}, (Day 1)} / T_{\text{min}, (Day -1)}$
-1	$T_{\text{max}}$
1	$T_{\text{max}}$
1	$T_{\text{max}} \text{ ratio: } T_{\text{max}, (Day 1)} / T_{\text{max}, (Day -1)}$

- 1  $AUC_{0-24}$  Area under the curve calculated by the trapezoidal rule for the time from 0 to 24 hours for the day given in the first column. For Day -1, take -0.5 and 0 hours of Day 1 as 23.5 and 24 hours of Day -1.
- 2  $AUC_{\text{partial}}$  ( $AUC_{2-8}$  and  $AUC_{2-12}$ ) Area under the curve calculated by the trapezoidal rule for the time from 2 to 8 and 2 to 12 hours for the day given in the first column.
- 3  $C_{\text{max}}$ ,  $C_{\text{min}}$  Concentration of FGF19 at the maximum or C4 at the minimum respectively for each subject from 0 to 24 hours for the day given in the first column. For Day -1, take -0.5 and 0 hours of Day 1 as 23.5 and 24 hours of Day -1.
- 4  $T_{\text{max}}$ ,  $T_{\text{min}}$  Time of maximum or minimum concentration of FGF19 or C4 respectively for each subject from 0 to 24 hours for the day given in the first column. For Day -1, take -0.5 and 0 hours of Day 1 as 23.5 and 24 hours of Day -1.

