## **PD Assessments**

### **Plasma and/or Serum PD Collection**

Blood samples will be collected relative to dosing of GS-9674 or PTM to measure PD biomarkers including but not limited to FGF19 (fibroblast growth factor 19) and 7-alpha-hydroxy-4-cholesten-3-one (C4) for GS-9674 at the following time points for each cohort:

- **Day -1:** -0.5, 0 (predose,  $\leq 5$  minutes prior to dosing), 0.25, 0.5, 1, 1.5, 2, 2.5, 3, 3.5, 4, 4.5, 5, 6, 8, 10, 12, and 16 hours post-dose (relative to Day 1 dosing time)
- **Day 1:** -0.5, 0 (pre-dose,  $\leq 5$  minutes prior to dosing), 0.25, 0.5, 1, 1.5, 2, 2.5, 3, 3.5, 4, 5, 6, 8, 10, 12, 16, 24, 48, 72, and 96 hours post-dose

A single blood sample will be collected for analysis including but not limited to bile acids at the following time point:

- **Day 1:** -0.5 hours predose

A blood sample for PD analysis will also be collected at the ET visit (if applicable) and may be analyzed.

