### 9.3. Statistical Analysis Methods

#### 9.3.1. General Considerations

Individual subject concentration data and individual subject PD parameters shown in [Table 9-1](#) will be listed and summarized using descriptive statistics by hepatic function group within each cohort. Summary statistics (numbers of subjects, geometric mean, 95% CI, %CV, median, minimum, maximum, Q1, and Q3) will be presented at specific time points as shown in [Table 9-1](#).

Individual concentration data listings and summaries will include all subjects with concentration data. The sample size for each time point will be based on the number of subjects with nonmissing concentration data at that time point.

Individual PD parameter data listings and summaries will include all subjects for whom PD parameters can be derived. The sample size for each PD parameter will be based on the number of subjects with nonmissing data for that PD parameter.

The following tables will be provided for each biomarker by hepatic function group within each cohort:

- PD concentrations and summary statistics
- PD parameters and summary statistics

The following figures will be provided for each biomarker by hepatic function group within each cohort:

- Mean ( $\pm$  SD) concentration data versus time on a linear (and semilogarithmic) scale for days -1 and 1.
- Boxplots of AUCs and AUC ratios as indicated in [Table 9-1](#) on a linear (and logarithmic) scale, categorized by days -1 and 1, and by hepatic function group.
- Boxplots of  $C_{\max}$  and  $C_{\max}$  ratios as indicated in [Table 9-1](#) on a linear (and logarithmic) scale, categorized by days -1 and 1, and by hepatic function group.
- Boxplots of  $C_{\min}$  and  $C_{\min}$  ratios as indicated in [Table 9-1](#) on a linear (and logarithmic) scale, categorized by days -1 and 1, and by hepatic function group.

The following listings will be provided:

- PD sampling details by subject, including procedures, differences in scheduled and actual draw times, and sample age.

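### SAP Table 9-1 takes Day 1/Day -1 ratios of PD Tmax and Tmin on a window that includes time 0, so these descriptive ratios can be undefined, zero or set by a sample label

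*SAP*

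**What the plan says.** SAP Table 9-1 lists Tmin and Tmax for Day -1 and for Day 1, and for each a ratio with Day 1 on top and Day -1 below. Footnote 4 defines them as the "Time of maximum or minimum concentration of FGF19 or C4 respectively for each subject from 0 to 24 hours" of the day concerned. The same footnote fills the end of the placebo day with the next morning's predose draws: "For Day -1, take -0.5 and 0 hours of Day 1 as 23.5 and 24 hours of Day -1".

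The SAP's PD collection schedule (section 1.3) has a 0 h draw on both days. The last draws belonging to Day -1 itself are at "4.5, 5, 6, 8, 10, 12, and 16 hours post-dose (relative to Day 1 dosing time"). SAP 9.1 says that the peak and trough times "will be determined empirically for the data". No rule is given for an extreme at 0 h, for ties, or for a zero in either part of the ratio.

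SAP 9.3.1 plans one set of statistics for the Table 9-1 parameters: "Summary statistics (numbers of subjects, geometric mean, 95% CI, %CV, median, minimum, maximum, Q1, and Q3"). SAP 9.2 says that parameters "will be generated for all subjects for whom parameters can be derived", and 9.3.1 sets the sample size separately for each parameter.

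**The concern.** Both markers are measured before any active drug is given, so a subject's highest FGF19 or lowest C4 value can be the predose value. The recorded time is then 0. A ratio cannot take 0 in the denominator, and a geometric mean cannot use a ratio of 0.

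The shared sample adds a labelling problem. The tube drawn just before the Day 1 dose is called 24 h on Day -1 and 0 h on Day 1. The ratio can therefore change sharply because of the name given to one sample, without any drug effect.

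At stake is how the timing of the FGF19 peak and the C4 nadir is reported. PD parameters are secondary endpoints, and each group is planned at 10 subjects for 8 evaluable, so one odd value is visible in a summary.

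**Working it through.** The plan states no figure for this point, so there is none to reproduce. The check lists every possible pair of times on the nominal sampling grid.

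**Inputs** (SAP 1.3 schedule and Table 9-1 footnote 4)
- Day -1 times: 0, 0.25, 0.5, 1, 1.5, 2, 2.5, 3, 3.5, 4, 4.5, 5, 6, 8, 10, 12, 16, then 23.5 and 24 borrowed from Day 1. That is 19 times.
- Day 1 times: 0, 0.25, 0.5, 1, 1.5, 2, 2.5, 3, 3.5, 4, 5, 6, 8, 10, 12, 16, 24. That is 17 times.
- Ratio R = T(Day 1) / T(Day -1). Number of pairs: 19 × 17 = 323.

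**Results**

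| Case | Pairs | R |
|---|---|---|
| T(Day -1) = 0 | 17 (one is 0/0) | undefined |
| T(Day 1) = 0, T(Day -1) > 0 | 18 | exactly 0 |
| Neither is 0, at least one at 23.5 or 24 h | 2 × 16 + 18 − 2 = 48 | 0.25/24 = 0.0104 to 24/0.25 = 96 |
| Both from 0.25 to 16 h | 16 × 15 = 240 | 0.25/16 = 0.0156 to 16/0.25 = 64 |

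The rows add to 17 + 18 + 48 + 240 = 323. These are counts of possible pairs, not probabilities.

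**Shared tube.** If the Day 1 predose sample is the extreme of both days, T is 24 on Day -1 and 0 on Day 1, so R = 0/24 = 0 for one and the same sample. If the Day 1 extreme is instead the next draw, 15 minutes after dosing, R = 0.25/24 = 0.0104.

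**Effect on the geometric mean** (illustration: all other subjects at R = 1.0)
- n = 10, one value of 0.0104: (1/96)^(1/10) = exp(−4.564/10) = 0.63.
- n = 10, one value of 96: 96^(1/10) = 1.58.
- n = 8: (1/96)^(1/8) = 0.57 and 96^(1/8) = 1.77.
- Any n, one value of 0: ln(0) is undefined, so the geometric mean is 0 or not computable, depending on the software.

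**Differences instead.** T(Day 1) − T(Day -1) is finite for all 323 pairs, from −24 to +24 h. The shared tube would still give 0 − 24 = −24 h, so a difference alone does not cure the double label.

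**The case against.** The strongest reply is that little depends on these rows. Table 9-2 compares AUC2-8, AUC2-12 and Cmax for FGF19, or Cmin for C4; it has no timing ratio. The boxplots in 9.3.1 cover AUC, Cmax and Cmin. The preliminary PD conclusion in Protocol 1.2.5.3 also rests on Cmax, Cmin and AUC2-12. Tmax and Tmin are reported for each day separately, so timing can be read without the ratio. The median and quartiles are already planned, and a single zero or extreme ratio barely moves them. All of this stands, and it makes the point minor.

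A reader might infer that subjects with a zero denominator are lost from the PD analysis, at 10% to 12.5% of a group each (1 of 10 or 1 of 8). The documents do not support that. Sample size is set per parameter, so one value leaves one ratio row and the subject stays everywhere else.

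The reply does not remove the defect. The wording on parameters that can be derived covers an undefined ratio. It does not cover a ratio of 0 or the 0 h/24 h double label.

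A reader might also call every late-edge ratio arbitrary. That goes too far: such ratios are finite, and 24/24 = 1 is sensible. Nor are 0 h and 24 h interchangeable on Day 1, since one precedes GS-9674 and the other follows it by 24 hours. Wide ratios also arise away from the edges (0.0156 to 64). Choosing a difference over a ratio is therefore partly preference; the zeros and the double label are the actual faults.

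**Conclusion.** The definition is faulty as written. Followed literally, it can give an undefined ratio, a ratio of 0 with no usable geometric mean, or 0/24 from one tube. The geometric mean of the daily Tmax and Tmin values fails in the same way when a time is 0.

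The size is small: descriptive PD timing rows only. A stronger inference, that the FXR-activation objective is compromised, is not supported, because its planned comparisons do not use these ratios. The primary PK analysis is untouched.

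The conclusion assumes nominal times. Footnote 4 points that way by naming the 0 h sample. If actual PD times were used, a draw a few minutes before dosing would have a slightly negative time, and the SAP does not say whether it would count; the rule setting predose times to zero is in the PK section (8.1). The shifts to 0.63 and 1.58 are worst-case grid values with all other subjects at 1.0. The documents hold no individual PD profiles, so the frequency of edge extremes is unknown.

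**What to change.** - In Table 9-1, replace the Tmax and Tmin ratios with the within-subject difference, Day 1 minus Day -1, in hours.
- In 9.3.1, summarise Tmax, Tmin and their differences with n, median, quartiles, minimum and maximum, without a geometric mean. This matches Protocol Table 1-2, which shows Tmax as median with quartiles.
- Keep the footnote 3 window for Cmax and Cmin, so that the reported time is the time of the reported extreme. Do not cut the timing window to 0.25–16 h: that would break this link and discard the real Day 1 24 h sample.
- Add one rule so that the shared predose sample cannot count as both Day -1 24 h and Day 1 0 h in a timing difference. It could be counted for one day only, or those subjects could be flagged. Flagging keeps each time tied to its reported extreme; counting it once means that the other day's time comes from the remaining samples.

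The cost is minor SAP wording and programming. The timing change is then read in hours and not as a ratio.
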